## 5.2 Primary output indicators

The following indicators will serve as the primary survey outputs:

1. prevalence of false-negative HRP2 RDT results caused by *pfhrp2/3* gene deletions among all symptomatic *P. falciparum* confirmed cases;
2. prevalence of suspected false-negative HRP2 RDT results (i.e. a negative HRP2 RDT result but a positive result by Pf-LDH RDT or *P. falciparum* microscopy, or HRP2-negative but Pf-LDH-positive in a serological test) among symptomatic patients with *P. falciparum* malaria; and
3. prevalence of *pfhrp2/3* gene deletions among symptomatic falciparum patients with a false-negative HRP2 RDT result.

The survey will identify the proportion of patients with suspected false-negative HRP2 RDT results through diagnostic testing at health facilities, using dual-method testing (HRP2 RDT plus microscopy or Pf-LDH RDT). To save time and resources, molecular +/- serological testing to confirm *P. falciparum* infection and identify *pfhrp2/3* deletions will prioritize DBSs collected from individuals with suspected false-negative HRP2 RDT results. Discordant diagnostic results may be due to other factors, such as false-positive Pf-LDH test lines (possibly due to cross-reactivity with non-falciparum species) or low parasite densities at

---

1 RDTs should be used that contain Pf-LDH-specific test lines and not pan-pLDH test lines. This will ensure that only *P. falciparum* infections are detected and avoid the identification of non-falciparum species (*P. vivax*, *P. malariae*, *P. ovale*), which would cause discordant results (HRP2-negative, pan-pLDH-positive).

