## 5.4 Statistical analysis plan and sample size

The aim of the statistical analysis is to identify survey domains (provinces, districts, states or similar) where there is a high probability that the prevalence of false-negative HRP2 RDT results caused by *pfhrp2* gene deletions is above 5%. Unlike previous versions of the protocol, here, the focus is on identifying areas that are above the threshold (one-tailed test), rather than above or below the threshold (two-tailed test).

Raw data consist of counts of the number of confirmed false-negative HRP2 RDT results caused by *pfhrp2* gene deletions (numerator) and the number of confirmed and enrolled *P. falciparum* cases (denominator) in each health facility. These can be fed into the software package DRpower, accessible via an interactive web app (<https://shiny.dide.ic.ac.uk/DRpower-app/>). This software uses a Bayesian hierarchical model to estimate the prevalence of false-negative HRP2 RDT results caused by *pfhrp2* gene deletions, while accounting for correlations within clusters (for more information on the model, see Annex 3). The software returns a point estimate of the prevalence along with a 95% credible interval (CrI). This information should be presented when summarizing results, but should not be used directly to decide whether a domain is above the threshold. That decision is based on another output of the software: the probability that the prevalence of false-negative HRP2 RDT results caused by *pfhrp2/3* deletions is above 5%. This value is used to categorize study domains as follows:

**Outcome 1:** The posterior probability of being above the 5% threshold is less than 0.95. In this case, there is not sufficient evidence to conclude that the proportion of false-negative HRP2 RDT results caused by *pfhrp2/3* deletions among symptomatic *P. falciparum* patients is greater than 5%.

**Outcome 2:** The posterior probability of being above the 5% threshold is greater than or equal to 0.95. In this case, there is high statistical confidence that the proportion of false-negative HRP2 RDT results caused by *pfhrp2/3* deletions among symptomatic *P. falciparum* patients is greater than 5%.

Programmatic decisions can be made on the basis of these outcomes. Note that it is possible for the CrI to span the 5% threshold when the probability of being above 5% is greater than 0.95 (because the CrI is two-tailed but the statistical test is one-tailed).

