  - A Pf-LDH RDT that meets WHO procurement criteria (Table 3) or microscopy can be used for the secondary diagnosis. Currently, there are no RDTs that meet the WHO performance criteria for detection of *P. falciparum* based on their Pf-LDH test line alone (29); therefore, for the purposes of screening patients in the survey, countries may exceptionally select Pf-LDH-based RDTs that (i) have been evaluated in WHO malaria RDT product testing; ii) meet performance criteria for detecting HRP2-expressing *P. falciparum*; and (iii) have a panel detection score (PDS) > 90 at 2000 parasites/μL, and false-positive and invalid rates < 2% (see Table 4).
  - If microscopy is to be used, one thin and one thick blood film should be prepared following national guidelines and aligned with the WHO standard operating procedures for malaria microscopy (30).

**Table 3. WHO-recommended malaria RDT options for detecting both HRP2-expressing and non-expressing *P. falciparum* malaria for *pfhrp2/3* gene deletion surveillance**

Performance criteria	A: P. falciparum PDS a ≥ 75% at 200 parasites/μL
	B: P. vivax PDS a ≥ 75% at 200 parasites/μL
	C: false-positive (FP) rate against clean negatives < 10%
	D: invalid rate (IR) < 5%
	E: pfhrp2 -negative P. falciparum PDS > 75% at 200 parasites/μL (in areas where pfhrp2 deletions are prevalent)

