**Table 4. Available non-WHO-prequalified tests meeting critical criteriaa**

Product name	Product code	Manufacturer name
Biocredit Malaria Ag Pf (pLDH)	C14RHG25, C14RHH25	Rapigen Inc.
Biocredit Malaria Ag Pf (pLDH/HRP2)	C13RHG25, C13RHH25	Rapigen Inc.
Biocredit Malaria Ag Pf/Pv (pLDH/pLDH)	C61RHG25, C61RHH25	Rapigen Inc.
CareStart™ Malaria Pf (HRP2/pLDH) Ag RDT	RMPM-02571	Access Bio Inc.
CareStart™ Malaria PAN (pLDH) Ag RDT	RMNM-02571	Access Bio Inc.

a Valid ISO 13485:2003, submission of application for WHO prequalification, and acceptable diagnostic performance against both HRP2-expressing and non-HRP2-expressing at 200 parasites/μL (*pfhrp2/3* single or double deletions), based on the most recent WHO laboratory assessment performed at the United States Centers for Disease Control and Prevention.

- For each consenting suspected malaria case, the health provider will attach a unique survey ID, chronologically ordered, to a survey case report form (Annex 7) and to the survey tally sheet (Annex 6). On the survey case report form, the health worker will record answers to questions regarding age, sex, and recent history of malaria diagnostic testing, treatment and travel.
  - Next, using the labels attached to the survey case report form (with the same ID number as the form), the health worker (treating clinician or laboratory worker) will label two different RDTs or one RDT and microscopy slide and a filter paper or protein saver card for DBS. The health worker will perform the tests, record the results on the survey case report form (Annex 7, sections 5–7), and either inform the patient of the results directly (clinician) or refer (laboratory worker) the patient back to the treating clinician for treatment in the case of positive test results on the primary or secondary RDT, or microscopy as per national guidelines. Results from either RDT should be acted upon, as both are WHO-prequalified. Microscopy is also considered an acceptable alternative to malaria RDTs. Negative RDT results should be managed as per national guidelines.
3. All used RDTs and, if applicable, microscopy slides from each consenting suspected malaria case will be stored until the survey is complete in a dry and protected area for survey quality control purposes.

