**REFERENCE LABORATORY USE ONLY**

17a.	Molecular analysis (Indicate the method chosen and make sure all the assay controls and analysis procedures are correctly followed)	
 
a. single copy gene 1 – present/absent/not done
 
b. single copy gene 2 – present/absent/not done
 
c. single copy gene 3 – present/absent/not done
 
d. HRP2 exon 1 – present/absent/not done
 
e. HRP2 exon 2 – present/absent/not done
 
f. HRP2 flanking 230 – present/absent/not done
 
g. HRP2 flanking 228 – present/absent/not done
 
h. HRP3 exon 1 present/absent/not done
 

17b.	Molecular method used	
 
a. Conventional PCR
 
b. Multiplex PCR
 
c. Digital PCR
 

18a.	Serology (indicate the method chosen and relevant controls used)	
 
a. pfhrp2+/pan-LDH+
 
b. pfhrp2-/pan-LDH-
 
c. pfhrp2+/pan-LDH-
 
d. pfhrp2-/pan-LDH+
 

18b.	Method of serological analysis	
 
a. Bead-based immunoassay
 
b. ELISA
 

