## Annex 8. Tabulation plan for prevalence of *pfhrp2/3* deletions

Characteristic	Suspected false-negative HRP2 RDT prevalence b (n=XX) (95% CI)	Confirmed pfhrp2/3 deletion prevalence c (n=XX) (95% CI)
Age in years		
<2		
3–5		
6–9		
10–19		
20–29		
30–39		
40–49		
50–59		
≥60		
Sex		
Male		
Female		
Location		
Urban		
Rural		
Domain (e.g. province, state)		
Domain 1		
Domain 2		
Domain 3		
Domain 4		
Domain 5		
Health facility (optional)		
Facility 1		
Facility 2		
Facility 3		
Facility 4		
Facility 5		
Facility 6		
Facility 7		
Facility 8		
Facility 9		
Facility 10		
Antimalarial treatment past 2 weeks		
Yes		
No		
Total		

- a Tabulations are based on *pfhrp2/3* deletion screening only in *P. falciparum* cases with discordant results. If all *P. falciparum* cases or all suspects are screened for *pfhrp2/3* deletions, then this form should be revised accordingly.
- b Suspected false-negative HRP2 RDT *P. falciparum* prevalence = # of discordant results (HRP2-negative & Pf-LDH- or microscopy-positive) / all *P. falciparum* cases confirmed by Pf-LDH RDT or microscopy as established under the protocol for this study.
- c *pfhrp2/3* deletion prevalence = # of *P. falciparum* cases with *pfhrp2/3* deletion causing false-negative HRP2 RDT results / total # of *P. falciparum* cases (Pf-LDH RDT-positive or microscopy-positive)

For further information please contact:

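### Table 4 lists a pan-pLDH test for survey screening against the section 5.2 footnote; where non-falciparum malaria occurs it would distort output 2 and, unless PCR-shown cases are removed, dilute output 1

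*Protocol*

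**What the plan says.** The footnote to Protocol section 5.2 states: "RDTs should be used that contain Pf-LDH-specific test lines and not pan-pLDH test lines". Its reason is that pan lines also pick up P. vivax, P. malariae and P. ovale, "which would cause discordant results (HRP2-negative, pan-pLDH-positive").

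Section 5.6 says that "for the purposes of screening patients in the survey, countries may exceptionally select Pf-LDH-based RDTs" meeting certain criteria, and points to Table 4. One of the five rows of Table 4 is "CareStart™ Malaria PAN (pLDH) Ag RDT". The note under the table covers quality certification, the prequalification application and performance on HRP2-expressing and non-expressing parasites. It says nothing about species specificity and does not refer back to the footnote.

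The counts that enter the DRpower model include "the number of confirmed and enrolled *P. falciparum* cases (denominator) in each health facility". The formulas in sections 5.6 and 5.10 define that denominator by a positive field Pf-LDH RDT or microscopy, and note c of Annex 8 does the same. The project summary (Data collection, step 9) lets enrolment stop at 30 such cases per facility.

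**The concern.** A country that follows section 5.6 to Table 4 can pick a product that the footnote advises against, and nothing at the table warns it. The example case report form (Annex 7, item 6) codes the second RDT only as negative or P. falciparum. A pan-positive P. vivax case recorded there would be entered as P. falciparum, and supervisor item S1 would class it as discordant.

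The numerator of output 1 is protected, because it requires a molecularly confirmed deletion in a P. falciparum case. The denominator has no matching written step. Output 2 is determined after data entry and before the laboratory work (section 5.10), so species PCR does not correct it as planned. Any error in output 1 is downward, towards missing a domain above 5%. The stake is the choice in section 5.6, items 10 and 11: a nationwide switch of RDTs if any domain reaches Outcome 2, or a repeat survey within two years if none does.

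**Working it through.** **Inputs from the Protocol.** 10 facilities × 30 cases (Table 2); true prevalence 10%, threshold 5%, Outcome 2 if the posterior probability is at least 0.95 (section 5.4); ICC 0.05 for simulation, uniform prior on prevalence, Beta(1,9) prior on the ICC (Annex 3).

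**Assumed.** f, the share of counted cases that are non-falciparum. The documents give no figure, so 5% to 40% is shown. For outputs 2 and 3, every deletion is taken to give a negative HRP2 RDT, with no other cause of discordance.

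**Step 1: reproduce Table 2.** Simulating the Annex 3 model (4,000 surveys per design) gives 80.6% power for 10 × 30, 81.5% for 9 × 37, 81.6% for 8 × 51, 80.7% for 7 × 68 and 80.1% for 6 × 113. All are within 2 points of the stated 80%, so Table 2 is not in question.

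**Step 2: effect on the three outputs if nothing is removed.**
- Output 1 = 10% × (1 − f)
- Output 2 = f + 10% × (1 − f)
- Output 3 = output 1 / output 2

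At f = 20%: output 1 = 10% × 0.8 = 8%; output 2 = 20% + 8% = 28%; output 3 = 8/28 = 29%.

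**Step 3: chance of Outcome 2.** Each of the 30 counted cases per facility is non-falciparum with probability f and can never enter the numerator (3,000 surveys per f). The data are analysed with the denominator left at 30, and again with the non-falciparum cases removed but not replaced.

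| f (assumed) | Output 1, kept | Output 2 | Output 3 | Chance of Outcome 2, kept | Chance of Outcome 2, removed |
|---|---|---|---|---|---|
| 0% | 10% | 10% | 100% | about 81% | about 81% |
| 5% | 9.5% | 14.5% | 66% | 76% | 80% |
| 10% | 9% | 19% | 47% | 70% | 79% |
| 20% | 8% | 28% | 29% | 58% | 79% |
| 30% | 7% | 37% | 19% | 39% | 76% |
| 40% | 6% | 46% | 13% | 22% | 74% |

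**Step 4: which true prevalences would read below 5%.** Observed prevalence is true prevalence × (1 − f), so the true value that reads as exactly 5% is 5% / (1 − f): 5.3%, 5.6%, 6.3%, 7.1% and 8.3% for f = 5%, 10%, 20%, 30% and 40%. For a true 10% to read as 5%, f would have to be 50%.

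**The case against.** The strongest reply is that the Protocol already catches these cases. A non-falciparum mono-infection that is pan-pLDH-positive and HRP2-negative is a discordant sample, and all discordant samples should go to molecular analysis (Table 1, note a). That work-up includes confirmation of P. falciparum (section 5.6, item 7) and species PCR (section 5.9.2.2). Output 1 is by definition a prevalence among confirmed P. falciparum cases, and section 5.4 advises a buffer for losses, naming diagnostic accuracy. This largely stands: the cases should be identified, and removing them recovers most of the power. What remains is that no formula says they are removed, and that output 2 is determined before PCR.

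A second reply is that the operative text, the formulas and the example form all presuppose a Pf-LDH line, and the form may be amended to suit the RDTs used. That is fair, and it means the harm requires a choice against the footnote. It also confirms that the Table 4 row does not belong with the rest of the text. The footnote says what should be done, so it is a recommendation rather than an absolute ban.

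Three stronger readings are tempting:
- A reader might infer that output 1 is pulled below 5%. At 10% true prevalence and f = 20% it reads 8%; only true values up to 6.25% would read 5% or less.
- A reader might take 58% as the survey's power under the pan test. It is one assumed point, with PCR-shown cases left in.
- A reader might infer that serology item 18a in Annex 7, which offers codes such as "pfhrp2+/pan-LDH", makes attribution to P. falciparum impossible. The footnote concerns RDT lines. In the standard survey, serology is optional support for genotyping (section 5.9.3), and species comes from PCR.

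**Conclusion.** The contradiction between Table 4 and the section 5.2 footnote is explicit and needs reconciling. Its consequence is conditional on a country selecting the pan product and on non-falciparum malaria occurring there. Given both, cases are counted wrongly in the field, output 2 rises and output 3 falls. At an assumed f of 10%, they read 19% and 47% instead of 10% and 100%, if deletions are the only other cause of discordance.

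Output 1 and the decision are harmed materially only under a third condition: that cases shown by PCR to be non-falciparum stay in the denominator. The chance of Outcome 2 at 10% true prevalence then drops from about 81% to 76%, 70%, 58%, 39% and 22% for f = 5%, 10%, 20%, 30% and 40%. With removal it is 80%, 79%, 79%, 76% and 74%. If f is near zero there is no effect. The text does not direct analysts to keep these cases; it fails to say that they leave.

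**What to change.** 1. Reconcile the two passages: remove the PAN row from Table 4, or mark it as not eligible as the survey's second test, with a reference to the section 5.2 footnote.
2. State in sections 5.6 and 5.10 and in Annex 8 that cases shown by species PCR not to be P. falciparum leave the denominator. This is worth having even after step 1, because section 5.2 itself notes that Pf-LDH lines can cross-react with other species.
3. Optionally, add a Pf-LDH option to item 18a, since output 2 refers to Pf-LDH in serology. Keep the pan-LDH codes: item 18b allows ELISA, and Annex 2 describes the commercial ELISA kits as measuring pan-pLDH.

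The cost is a table edit and a few sentences. One listed product is lost; four others and microscopy remain. Denominators become slightly smaller, which costs about 2 points of power at f = 20% (about 79% against 81%).

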  - Molecular-based confirmation of *pfhrp2/3* deletions is needed to ensure that discordant results are caused by *pfhrp2/3* gene deletions and not by other factors, such as operator error, false-positive Pf-LDH test lines, false-positive microscopy results, or samples at the limit of detection of the RDTs, which may not always react sufficiently to generate a positive test line. The contribution of these alternative causes of discordant results will vary.
  - Serological confirmation of *pfhrp2/3* gene deletions may also be performed using immunoassays, especially on samples where there is lack of agreement between RDT and PCR results.
8. Once the true number of cases with false-negative HRP2 RDT results caused by *pfhrp2* gene deletions is known, the prevalence at the domain level can be calculated for each sampling domain (e.g. province, state), using the DRpower software or interactive web app (<https://shiny.dide.ic.ac.uk/DRpower-app/>). This software also calculates a 95% CrI around this estimate (see Annex 3). The raw calculation is based on the formula:

$$\text{Proportion of } P. \text{ falciparum} \text{ cases with false-negative HRP2 RDT results due to } pfhrp2/3 \text{ deletions} = \frac{\text{\# of confirmed } P. \text{ falciparum} \text{ cases with } pfhrp2/3 \text{ gene deletions and HRP2-RDT negative results}}{\text{\# of confirmed } P. \text{ falciparum} \text{ cases (positive by either Pf-LDH RDT or microscopy)}}$$

9. Statistical analysis in DRpower will also result in an estimate of the probability that the prevalence of false-negative HRP2 RDT results caused by *pfhrp2/3* gene deletions is above 5%. This will result in one of two outcomes per domain:

**Outcome 1:** The posterior probability of being above the 5% threshold is less than 0.95. In this case, there is not sufficient evidence to conclude that the proportion of false-negative RDT results caused by *pfhrp2/3* gene deletions among symptomatic *P. falciparum* patients is greater than 5%.

**Outcome 2:** The posterior probability of being above the 5% threshold is greater than or equal to 0.95. In this case, there is high statistical confidence that the proportion of false-negative HRP2 RDT results caused by *pfhrp2/3* gene deletions among symptomatic *P. falciparum* patients is greater than 5%.

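### Output 1 sets PCR-confirmed deletions against a field-test denominator that keeps discordant cases PCR shows are not P. falciparum, so the prevalence compared with 5% is biased downward, slightly at 40% positivity and materially only if positivity is low

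*Protocol*

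**What the plan says.** Section 5.6, step 8 gives the output 1 formula, and section 5.10 repeats it. The numerator counts confirmed P. falciparum cases with pfhrp2/3 "gene deletions and HRP2-RDT negative results". The denominator is the number of confirmed P. falciparum "cases (positive by either Pf-LDH RDT or microscopy". Annex 8, footnote c uses the same population: "Pf-LDH RDT-positive or microscopy-positive". Annex 2, section 4 has a parallel formula for immunoassay surveys. Section 5.4 makes the count of confirmed and enrolled cases the "denominator) in each health facility" that is entered in DRpower. In all these places, confirmed means positive on the field test or, in Annex 2, possibly on the immunoassay. It never means positive by PCR.

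The protocol also expects some of these cases not to be falciparum malaria. Section 5.2 says: "Discordant diagnostic results may be due to other factors, such as false-positive Pf-LDH test lines". Section 5.6, step 7 lists "false-positive Pf-LDH test lines, false-positive microscopy results" among the reasons for molecular confirmation. That step sends samples for P. falciparum confirmatory testing, and section 5.9.2.2 calls for species-specific PCR. For Pf-LDH RDTs admitted by the exceptional route, section 5.6 requires "false-positive and invalid rates < 2% (see Table 4"). Table 3 carries a general false-positive limit of below 10%.

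The conclusion attached to each outcome is worded as a proportion among symptomatic P. falciparum patients (sections 5.4 and 5.6, step 9).

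**The concern.** A discordant case that PCR shows is not P. falciparum cannot carry a pfhrp2/3 deletion. It can never enter the numerator, yet it stays in the denominator. The error therefore has one direction: the ratio understates the proportion among P. falciparum patients, which is the proportion the conclusion names.

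The ratio drives a consequential decision. Under section 5.6, steps 10 and 11, Outcome 2 in any domain leads to a nationwide change of RDTs, while Outcome 1 in all domains leads to a repeat survey within two years. Section 5.6 also asks that low-transmission zones be included. For a fixed false-positive rate, false positives form a larger share of all positives where few patients are truly infected. The protocol does not say this, but it follows by arithmetic.

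**Working it through.** **Reproducing Table 2.** The Annex 3 model was coded: beta-binomial counts, uniform prior on prevalence, Beta(1, 9) prior on the ICC, and Outcome 2 if Pr(p > 0.05) is at least 0.95. Data were simulated at prevalence 10% and ICC 0.05, with 2,000 to 4,000 surveys per design. Power was 80.6% for 10 × 30, 81.5% for 9 × 37, 81.6% for 8 × 51, 81.0% for 7 × 68 and 80.6% for 6 × 113. These agree with the stated 80% (the 5 × 496 row was not run). The default design has almost no margin.

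**Share of false positives.** Let T be test positivity, FPR the false-positive rate and Se the sensitivity of the Pf-LDH RDT. True positivity is π = (T − FPR)/(Se − FPR), and the false share of the denominator is f = (1 − π) × FPR/T. The expected raw prevalence is the true prevalence × (1 − f).

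Inputs: T = 40% is the example in section 5.4. T = 20%, 10% and 5% are assumptions for lower transmission. FPR = 2% is the ceiling in section 5.6, and 1% is an assumed value below it. Se = 1 is an assumption; at FPR 2%, taking Se = 0.75 lowers f by less than one percentage point.

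Example at T = 10%, FPR = 2%: π = 0.08/0.98 = 0.0816, so f = 0.9184 × 0.02/0.10 = 0.184. Of 300 enrolled, about 55 are not P. falciparum and 245 are. At a true 10% there are about 24.5 confirmed cases: 24.5/300 = 8.2% as written, 24.5/245 = 10% after removal.

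| T | f at FPR 1% | f at FPR 2% | True 10% reads as (FPR 1%; 2%) |
|---|---|---|---|
| 40% | 1.5% | 3.1% | 9.8%; 9.7% |
| 20% | 4.0% | 8.2% | 9.6%; 9.2% |
| 10% | 9.1% | 18.4% | 9.1%; 8.2% |
| 5% | 19.2% | 38.8% | 8.1%; 6.1% |

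The true prevalence at which the ratio as written equals 5% is 0.05/(1 − f). At FPR 2% this is 5.2% at T = 40%, 6.1% at T = 10% and 8.2% at T = 5%. At Table 3's general limit of 10%, f would be 17% at T = 40% and 44% at T = 20%, so a true 10% would read as 8.3% and 5.6%.

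**Chance of Outcome 2 at a true 10%** (10 × 30 enrolled, ICC 0.05, every false positive discordant and identified by PCR):

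| f | As written | PCR-excluded cases removed |
|---|---|---|
| 3% | 80% | 81% |
| 8% | 73% | 80% |
| 18% | 60% | 79% |
| 39% | 24% | 75% |

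Separate runs agree within simulation error: 79% versus 82% at f = 3%, 58% versus 77% at f = 18%, and 24% versus 75% at f = 39%. Intermediate values follow the same pattern: 71% versus 80% at f = 10%, 56% versus 78% at f = 20%, and 39% versus 76% at f = 30%.

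**The case against.** **The effect is small at the protocol's own figures.** This stands. The only positivity given is 40%, as an example. With a false-positive rate at the 2% ceiling, a true 10% reads as 9.7% and power is essentially unchanged. The large losses need positivity of 10% or less, which is assumed here, and a rate at a limit that is written as an upper bound. A reader might infer that every survey is badly underpowered; the documents do not support that.

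**Output 3 should be left alone.** This also stands. A reader might infer that the same cases wrongly depress output 3. Section 5.10 says that ratio indicates the predictive value of a false-negative HRP2 RDT result, and objective 4 in section 3 asks for the same. A predictive value must keep the screen's false alarms in its denominator, and removing them would inflate it. Section 5.2 words output 3 as being among falciparum patients. That is a tension in wording, not a reason to change the formula.

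**Microscopy is not covered.** The protocol gives no false-positive rate for microscopy, the project summary requires it to be quality-assured, and the case report form provides for two national-laboratory cross-check reads. The figures above cannot be carried over to microscopy-based surveys.

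**False positives need not all be HRP2-negative.** The protocol does not say that they are, and Table 1 recognises HRP2 that persists after an infection has resolved. HRP2-positive, Pf-LDH-positive samples are not routinely sent for molecular testing, so any false positives among them would remain after the fix.

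**Does the protocol already cover the point?** It does not. The lower-limit remark in section 5.2 concerns deletions that the testing misses, not an inflated denominator. The buffer for diagnostic accuracy in section 5.4 implies that cases are lost, but no formula removes them. Annex 6 asks that the counting method be fixed beforehand, but offers only Pf-LDH RDT or microscopy.

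**Conclusion.** The point holds for output 1. A PCR-based numerator is divided by a field-test denominator, no sentence removes discordant cases that PCR excludes as P. falciparum, and the ratio compared with 5% is multiplied by (1 − f). The direction is certain, because such cases can only enlarge the denominator.

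The size is not certain. It is minor at 40% positivity with a false-positive rate of 1–2%, and material at an assumed positivity of 10% or less. It rests on the assumed rate and positivity, on near-full sensitivity, and on false positives being discordant and therefore PCR-tested. This is a should-fix: the decision quantity does not match the population named in its own conclusion, but serious loss of power depends on conditions that the protocol does not state.

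**What to change.** For output 1 only, define each facility's denominator as field-test positives minus discordant samples that species PCR shows are not P. falciparum. Make the change in section 5.4 (DRpower input), section 5.6 step 8, section 5.10, Annex 8 footnote c and the parallel formula in Annex 2, section 4.

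- Remove a sample only if the DNA quality controls of sections 5.9.2.1 and 5.9.2.3 are passed. Samples with failed or degraded DNA stay in; otherwise true cases would be dropped and the prevalence overstated.
- Report the removed cases separately, and give the result with the field-test denominator as a sensitivity analysis.
- Leave the output 2 and output 3 denominators as measures of field discordance.

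The PCR on discordant samples is already planned, so the analysis cost is mainly wording. There is also an enrolment cost. Facilities stop at 30 field-test positives, before PCR, so facility counts become smaller and unequal (DRpower accepts this), and power falls slightly below 80% when f is large: 79% at f = 18%, 75% at f = 39%. The buffer in section 5.4 should be sized to cover the removals. Keeping 30 cases per facility needs 30/(1 − f) field-test positives on average: 31 at f = 3.1%, 33 at 8.2%, 37 at 18.4% and 49 at 38.8%, rounded up. False positives that are also HRP2-positive would remain.
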